#### **Definition of Adverse Event of Special Interest**

For the purposes of the study, the primary AESIs will be those related HPA axis suppression. Subjects will be observed carefully for any evidence of systemic corticosteroid effects such as hypercorticism and adrenal suppression. Serum cortisol levels will be measured and will be the primary evaluator of any potential HPA axis suppression (see Section 6.3.4). Oral and esophageal candidiasis will however be considered AEs of special interest. Subjects may remain in the study during the treatment for these AEs. The Investigator may allow swish and spit 30 minutes after dosing for these subjects. Subjects must be instructed not to swallow the rinsing water. Adverse events related to such effects will be considered AESIs for the purposes of the study.

#### 6.3.1.1 Severity and Relationship of Adverse Events

#### Severity

The severity of the all AEs will be characterized as "mild, moderate, or severe" according to the following definitions:

• Mild events are usually transient and do not interfere with the subject's daily activities;

- Moderate events introduce a low level of inconvenience or concern to the subject and may interfere with daily activities;
- Severe events interrupt the subject's usual daily activity.

#### **Relationship (Serious Adverse Events Only)**

Documentation for SAEs only will involve the Investigator making a causality assessment. To promote consistency among Investigators, the guidelines in Table 6-1 should be taken into consideration, along with good clinical judgment, when determining the relationship of study drug to AE.

**Table 6-1 Relatedness of SAEs** 

Not related	The SAE is definitely not associated with study drug AND/OR;	
	The SAE does not follow a reasonable temporal sequence from study drug administration AND/OR;	
	The SAE does not disappear or decrease on discontinuation of the study drug (dechallenge) and/or does not reappear or increase on repeated exposure (rechallenge) AND/OR;	
	The SAE is reasonably explained by known characteristics of the subject's clinical state, history, environment, other therapy administered to the subject (drug or nondrug) AND/OR;	
	The SAE may be caused by reasons other than administration of the study drug.	
Related	The SAE follows or may follow a reasonable temporal sequence from study drug AND/OR;	
	The SAE disappears or abates upon discontinuation of study drug (dechallenge) and/or reappears or increases on repeated exposure (rechallenge) AND/OR;	
	The SAE cannot be reasonably explained by known characteristics of the subject's clinical state, history, environment, other therapy administered to the subject (drug or nondrug) AND/OR;	
	Previous experience with the study drug or related compounds resulted in a similar event AND/OR;	
	The SAE is a known effect of APT-1011.	

Abbreviation: SAE = serious adverse event.

#### 6.3.1.2 Recording and Reporting of Adverse Events

An AE must be promptly documented and recorded on the Adverse Events eCRF. The Investigator is responsible for recording all AEs observed or reported during the study, regardless of causality and/or clinical significance.

At each study visit, after the subject has had an opportunity to spontaneously mention any problems, the Investigator or designee should inquire about AEs by asking the appropriate open questions. In addition to straightforward subject observation (e.g., headache, nausea, etc.), AEs will also be documented from any data collected in the eCRF (e.g., laboratory values, physical examination findings, etc.) or other documents (e.g., subject diaries) that are relevant to subject safety.

The Adverse Event eCRF will record the following information.

- Name of the AE;
  - o Investigators should use correct medical terminology/concepts when recording AEs in the Adverse Event eCRF, avoiding colloquialisms and abbreviations.
  - Only 1 AE term should be recorded in the event field on the Adverse Event eCRF. If several conditions meet the criteria for AE reporting, each condition should be reported in the separate eCRF.
  - o If known, a diagnosis should be recorded on the Adverse Event eCRF rather than individual signs and symptoms (e.g., record only hepatic injury or hepatitis rather than jaundice and elevated transaminases). However, if a constellation of signs and/or symptoms cannot be medically characterized as a single diagnosis or syndrome at the time of reporting, each individual event should be separately recorded on the Adverse Event eCRF. If a diagnosis is subsequently established, all previously reported AEs based on signs and symptoms should be replaced by a single AE report based on the single diagnosis, with a starting date that corresponds to the starting date of the first symptom of the eventual diagnosis. Signs/symptoms of the reported AE should be described in the eCRF description field.
- Date of onset of the AE;
- Intensity (mild, moderate, or severe);
- Date of resolution (or statement that the event is ongoing);
- Action taken;
  - Concomitant medication or adjunctive therapy/procedure given will be recorded on the concomitant medication form or adjunctive therapy/procedure form of the eCRF, respectively.
- Subject outcome;
- Whether the event meets the definition of an SAE.

The CRA will check the completeness and accuracy of the Adverse Events eCRF. Wherever possible, all AEs regardless of the seriousness must be followed through resolution.

#### 6.3.1.2.1 Timing of Expected Reporting of Adverse Events

All AEs should be reported from the time of signature on the ICF to the last study visit.

All SAEs should be reported from the time of signature of the ICF to 30 days after the last study procedure or study drug administration.

86

#### 6.3.1.2.2 Expedited and Other Notable Reporting of Nonserious Adverse Events

In addition to the expedited reporting requirements for SAEs, the following events will be recorded and reported within 24 hours to the Sponsor (similar to reporting requirements for SAEs to the Sponsor [see Section 6.3.1.3]):

- Any pregnancy that occurs in subjects or their partners during the study;
  - o Follow-up should be completed to collect information about the course of the pregnancy, delivery, and condition of the newborn and this information provided to the Sponsor in a timely manner. If the newborn is healthy, additional follow-up is not needed. In case of a health problem in the newborn, follow-up must be performed.
- Drug abuse, misuse, and overdose with or without AEs (an overdose is a dose higher than that prescribed by a health care professional for clinical reasons);
  - The Investigator will use their clinical judgement to decide whether a dose was an overdose.
- Inadvertent or accidental exposure to the study drug with or without an AE;
- Any other medication errors (including dispensing errors such as inadvertent use of expired medication and dosing errors) with or without an AE.

Specific forms for reporting these events will be included in the ISF. These data will also be recorded in the eCRF.

#### 6.3.1.3 Reporting of Serious Adverse Events to the Sponsor

Serious adverse events will be monitored by the Sponsor in real time throughout the study.

All SAEs, regardless of relationship to study drug, must be reported by the Investigator to the Sponsor by completing the electronic Serious Adverse Event eCRF within 24 hours of awareness. This includes SAEs occurring as soon as the subject signs the ICF (i.e., pretreatment SAEs). The Serious Adverse Event eCRF should be completed as thoroughly as possible, given the information available and time constraints, and then signed electronically by the Investigator.

In case of unavailability of the electronic capture (EDC) database, the SAE should still be reported to the Sponsor within 24 hours of awareness using the paper Serious Adverse Events Form provided in the ISF. The paper Serious Adverse Events Form should be faxed or emailed to the Sponsor or designee.

If any follow-up information is received after the last study procedure or last study drug administration, this information will not be recorded in the eCRF but should be provided to the Sponsor using the paper Serious Adverse Events Form. Additionally, any new spontaneously reported SAEs that occur within 30 days after the last study procedure or study drug administration should be recorded in the paper Serious Adverse Events Form.

## 6.3.1.4 Reporting of Serious Adverse Events to Regulatory Authorities and Investigators

In addition to these reporting requirements of SAEs to the Sponsor or designee, every Investigator is expected to know, understand, and follow reporting procedures according to their local reporting requirements and IRB/IEC requests.

Investigators will be notified by the Sponsor or designee of all SAEs that require prompt submission to their IRB/IEC. Investigators should provide written documentation of IRB/IEC notification for each report to the Sponsor or designee. The Sponsor or designee will ensure that all SAEs are reported to the appropriate regulatory authorities.

## 6.3.1.5 Follow-Up of Adverse Events

Any AEs observed from Screening up to the end of the study will be followed up to resolution. Resolution means that the subject has returned to a baseline state of health or the Investigator does not expect any further improvement or worsening of the AE. All AEs that occur after the subject completes the study should also be reported to the Sponsor or designee within 30 days of the last dose of study drug.

#### **6.3.1.5.1** Nonserious Adverse Events

Whenever possible, all AEs that occur during the study, regardless of the seriousness, must be followed to satisfactory resolution or until the Investigator or designee deems the event to be chronic or not clinically significant or the subject to be stable.

#### 6.3.1.5.2 Serious Adverse Events

A subject experiencing 1 or more SAEs will receive treatment and follow-up after evaluation by the Investigator, or will be referred to another appropriate physician for treatment and follow-up. Discontinuation from the study and all therapeutic measures will be at the discretion of the Investigator.

The clinical condition of subjects who have had an SAE must be followed until all parameters, including laboratory values, have either returned to normal or to baseline value or are otherwise explained or judged acceptable by the Investigator. Follow-up and/or final reports, including information on the action taken and the outcome, must be sent to the Sponsor.

APT-1011

In the event of death, any post-mortem findings (including histopathology and autopsy reports) must be provided to the Sponsor.

#### 6.3.1.5.3 Adverse Events of Special Interest

The primary AESIs for FLUTE are events related HPA axis suppression (see Section 6.3.4).

APT-1011 (fluticasone proprionate ODT) a minimally absorbed corticosteroid is expected to act topically in the esophagus. Because of this, there is potential for decreased efficacy if the subject swallows water soon after dosing. Since the use of fluticasone has only been rarely associated with oral candidiasis there will be no need to do swish and spit since this could inadvertently be associated with swallowed water.

Oral and esophageal candidiasis will however be considered AESIs. Subjects may remain in the study during the treatment for these AESIs. The Investigator may allow swish and spit 30 minutes after dosing for these subjects. Subjects must be instructed not to swallow the rinsing water.

These will be followed until resolution or until judged to be acceptable by the Investigator.

#### 6.3.2 Clinical Laboratory Evaluations

Blood and urine samples are to be taken as close as possible to 0800 hours. The blood draw for morning serum cortisol may be drawn  $\pm 3$  days of scheduled visit to accommodate accurate timing. Other laboratory blood draws scheduled for the visit may be done at the same time.

Q2 Solutions will be the responsible central laboratory.

Clinical laboratory tests will be reviewed for results of potential clinical significance at all time points throughout the study. The Investigator will be required to comment on any laboratory values outside the normal reference range, as well as evaluate any change in laboratory values. Laboratory values substantially out of range and within laboratory alert ranges should be evaluated promptly.

Laboratory values outside the normal range that are considered clinically significant by the Investigator upon repeat testing and are significantly changed from baseline, should be considered an AE. If the abnormal laboratory value is consistent with a current diagnosis, it may be documented accordingly. All laboratory value abnormalities that require medical treatment should be considered an AE.

#### 6.3.2.1 Serum Chemistry

The following will be assessed: sodium, potassium, chloride, calcium, magnesium, phosphorus, blood urea nitrogen, creatinine, glucose, albumin, total protein, alkaline phosphatase, total

bilirubin, direct bilirubin (if total bilirubin >1.5 mg/dL), aspartate transaminase (AST), alanine transaminase (ALT), and 5'-nucleotidase (if alkaline phosphatase exceeds upper limit of normal (ULN).

89

Elevated liver function tests potentially meeting Hy's Law must be evaluated immediately, and the Sponsor must be notified of a potential case immediately to obtain further instructions. For the purposes of FLUTE, Hy's Law parameters will be ALT or AST  $\geq$ 3x ULN and total bilirubin  $\geq$ 2x ULN. A true Hy's Law case with this elevation of liver enzymes without an alternative explanation other than drug-induced liver disease should be reported as an SAE. All potential Hy's Law cases will be followed until resolution.

#### 6.3.2.2 Hematology

The following will be assessed: red blood cell (RBC) count, hemoglobin, hematocrit, mean corpuscular volume, mean corpuscular hemoglobin, mean corpuscular hemoglobin concentration, white blood cell (WBC) count and differential, absolute neutrophil count, and platelet count.

### 6.3.2.3 Urinalysis

The following will be assessed: dipstick-measured pH, specific gravity, total protein, ketones, glucose, nitrite, leukocyte esterase activity, bilirubin, and microscopic analysis (RBC, WBC, and urinary casts).

#### 6.3.2.4 Other Laboratory Evaluations

#### **Pregnancy Test**

Females of childbearing potential are required to be tested for pregnancy by the urine  $\beta$ -human chorionic gonadotropin test. Serum pregnancy test should be completed at Screening and urine pregnancy test thereafter.

#### Follicle-stimulating Hormone and Luteinizing Hormone

Females of non-childbearing potential ≤65 years of age will be tested for FSH/LH to confirm menopause.

Once non-childbearing potential and/or menopause is confirmed, further pregnancy tests are not required.

#### **Serum Cortisol (Morning Fasting)**

Subjects must be fasting for an 8-hour period prior to the serum cortisol assessments.

See also Section 6.3.4.

#### ACTH Stimulation Test (250 μg)

If any subject's morning serum cortisol is  $<5~\mu g/dL$  at Screening, falls to below that level during the study, and/or there are signs and symptoms of hypercorticism, an ACTH stimulation test (60 minute with 250  $\mu g$ , following the procedure from a commercialized test kit) will be required to rule out or confirm adrenal suppression.

This test will also be performed at Screening prior to Visit 2 (4-week Baseline Symptom Assessment), as well as at Visit 6 (Week 12), Visit 10 (Week 26) and Visit 14 (Week 52). It may also be performed in the event of clinical symptoms or a low cortisol result.

See also Section 6.3.4.

#### Serology

HIV 1 and HIV 2 DNA by PCR will be performed at Screening. Subjects with positive results will be excluded. HBsAg, anti-HBs and total anti-HBc (if positive, HBV DNA will be done) will assessed. Subjects with positive HBsAg, positive anti-HBc with positive HBV DNA) will be excluded. Anti-HBs positive alone, which is indicative of prior cleared infection or vaccination is allowed.

Anti-HCV will be confirmed by HCV RNA. Subjects with positive HCV RNA will be excluded.

#### HbA1C

HbA1C should be performed on all subjects with diabetes during Screening to assess level of control. This may be repeated as needed throughout the study.

#### 6.3.3 Physical Examination and Vital Signs

Physical examinations will be used to detect and evaluate AEs, but are not a safety variable for analysis.

Physical examination will include assessments of weight, general appearance, head and neck, eyes and ears, nose and throat, chest, lungs, heart, abdomen, extremities and joints, lymph nodes, skin, and age-appropriate neurological examination. Genitourinary and rectal examinations are not required unless there is a specific complaint.

Vital signs to be collected include pulse (after a 5-minute rest in sitting position), respiratory rate, temperature (°C), and blood pressure (after a 5-minute rest in sitting position and measured from the same arm throughout the study).

#### 6.3.4 Cortisol-related Findings

All subjects will undergo a 250 µg ACTH stimulation test during the Screening period.

At all visits (scheduled or unscheduled), specific attention will be given to potential changes related to corticosteroids, as well as symptoms of hypercorticism (Appendix 6). Should a subject undergo surgery or trauma during the study, particular care should be taken in observing subjects for evidence of inadequate adrenal response. These assessments must be documented in the eCRF.

If hypercorticism or adrenal suppression are suspected, an adequate work-up should be performed to confirm or rule out these findings. Specifically, to monitor for HPA axis suppression of potential clinical concern, a 250  $\mu$ g ACTH stimulation test will be performed after Screening if any of the following occur:

- During routine laboratory testing completed for the study, the subject has a morning serum cortisol level  $\leq 5 \,\mu g/dL$  ( $\leq 138 \,\text{nmol/L}$ ) (confirmed by 2 blood draws), including at the last ontreatment visit for a subject (ACTH stimulation test to be completed at an unscheduled visit);
  - See Section 6.3.4.1 for a discussion of the expected management/treatment of abnormal serum cortisol levels for the purposes of the study.
- The subject reports symptoms of hypercorticism (Appendix 6) (ACTH stimulation test to be completed at an unscheduled visit if needed).
- The subject discontinues due to HPA axis suppression (ACTH stimulation test to be completed at the Early Termination Visit).

An abnormal result for the ACTH stimulation test is defined as serum cortisol level <16 µg/dL (440 nmol/L) at 60 minutes after treatment with 250 µg cosyntropin administered intramuscularly. This result is exclusionary (see Section 4.2.2) if it occurs at Screening/4-week Baseline Symptom Assessment and requires follow-up through recovery of adrenal function if it occurs thereafter. The Sponsor will provide guidelines for safety follow-up (see Section 6.3.4.1) and document of restoration of adrenal function in all subjects demonstrating evidence of hypercorticism or HPA axis suppression during the course of the study.

Any clinical (Appendix 6) or laboratory abnormalities reflecting potential cortisol issues (such as abnormal morning cortisol, urinary glucose, or elevated serum glucose and results of ACTH stimulation test) will also be reported on a cortisol-specific eCRF. Changes fulfilling the definition of an AE, including laboratory values related to cortisol, will be reported as AEs in the eCRF.

All subjects will have an ACTH stimulation test performed at Screening, Week 12 (Visit 6), Week 26 (Visit 10), Week 52 (Visit 14), and at the end of treatment. It may also be performed in the event clinical symptoms or a low cortisol result.

#### 6.3.4.1 Management

If the subject has serum cortisol  $\leq 5 \mu g/dL$  (138 nmol/L) and

- The subject is asymptomatic: An ACTH stimulation test will be performed within the following week to confirm adequacy of adrenal reserve. The ACTH stimulation test may be performed at any time of the day and does not require subjects to be in fasting state. If the test suggests adrenal insufficiency (i.e., minimum cortisol value <16 µg/dL [440 nmol/L] before or 30 minutes after ACTH injection), the subject will be prescribed CORTEF® (hydrocortisone oral) 10 mg/day in the morning and be referred to an endocrinologist for further monitoring and management. The Investigator will maintain contact with the subject and endocrinologist on a biweekly basis until adrenal insufficiency is resolved or determined to be unrelated to study participation. If the test does not suggest adrenal insufficiency, no further follow-up is required.
- The subject is symptomatic (Appendix 6): The subject will be prescribed CORTEF® (hydrocortisone oral) 10 mg/day in the morning and be referred to an endocrinologist for further monitoring and management. The Investigator will maintain contact with the subject and endocrinologist on a biweekly basis until adrenal insufficiency is resolved or determined to be unrelated to study participation.

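### Protocol 6.3.4.1 decides on hydrocortisone from ACTH-test samples at 0 or 30 minutes, while 6.3.4 and Exclusion 24 define an abnormal test at 60 minutes, so one test can be classified both ways

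*Protocol*

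**What the plan says.** **Definition.** Protocol 6.3.4 states: "An abnormal result for the ACTH stimulation test is defined as serum cortisol level" below 16 µg/dL (440 nmol/L), measured "at 60 minutes after treatment with 250" µg of cosyntropin. Exclusion Criterion 24, the cortisol part of the synopsis and footnote r of Table 4-1 agree. Section 6.3.2.4 also describes a 60-minute test, "following the procedure from a commercialized test kit". After Screening, 6.3.4 requires follow-up of an abnormal result until adrenal function has recovered.

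**Management.** Section 6.3.4.1 opens with the condition "If the subject has serum cortisol" of 5 µg/dL (138 nmol/L) or less. For asymptomatic subjects it continues: "An ACTH stimulation test will be performed within the following week to confirm adequacy of adrenal reserve". The test suggests insufficiency if the minimum cortisol is below 16 µg/dL "before or 30 minutes after ACTH injection". If so, hydrocortisone is prescribed and the subject is referred to an endocrinologist; if not, follow-up ends. No 60-minute value is mentioned. Symptomatic subjects are prescribed hydrocortisone without waiting for a test.

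**Analysis.** The safety endpoint is a composite: cortisol of 5 µg/dL or less, or an abnormal ACTH test. The synopsis writes the ACTH part as <16 µg/dL with ≤440 nmol/L at 60 minutes. Protocol 6.3.6 writes ≤16 at 60 minutes. SAP 17.6 writes ≤16 with no sampling time.

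**The concern.** The two sections govern the same subjects: 6.3.4 sends the reader to 6.3.4.1 twice, once for handling abnormal cortisol and once for safety follow-up. Yet they read different samples from the same test, and 6.3.4.1 adds the unstimulated value. Because entry to 6.3.4.1 requires a low cortisol, an unstimulated value in the rule can decide the outcome before the stimulated response is considered.

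What is at stake:

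- **Treatment and follow-up.** The 6.3.4.1 sentence separates a systemic steroid with referral from no further action. Events related to HPA axis suppression are the primary adverse events of special interest (Protocol 6.3.1).
- **Reporting.** SAP 17.6 counts discontinuations for an abnormal ACTH test separately, so what counts as abnormal must be fixed.
- **Prohibited medication.** Protocol 5.8.2 prohibits corticosteroids during the study and records even short use for specific adverse events as a deviation. SAP 5.4 lists prohibited treatment that may affect efficacy as a potential per-protocol exclusion. The protocol may thus direct use that it elsewhere treats as a deviation, in subjects whose test is normal by 6.3.4.

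Protocol 5.7 blinds cortisol values to sites after randomization and relies on programmed alerts, which makes it less likely that site judgement resolves the ambiguity.

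**Working it through.** The plan gives no figure to reproduce here. The check compares the two rules and adds simple arithmetic.

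**1. Units.** 138/5 = 27.6 and 440/16 = 27.5. The conversions agree within rounding, so the conflict is not a unit artefact.

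**2. Rules side by side.** Write C0, C30 and C60 for cortisol (µg/dL) before injection and at 30 and 60 minutes.

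- Section 6.3.4: abnormal if C60 < 16.
- Section 6.3.4.1, literal reading: insufficient if min(C0, C30) < 16.
- Section 6.3.4.1, charitable reading (neither value reaches 16): insufficient if max(C0, C30) < 16.

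| C0, C30, C60 | 6.3.4 | 6.3.4.1 literal | 6.3.4.1 charitable |
|---|---|---|---|
| 5, 17, 20 | normal (20 ≥ 16) | insufficient (min 5) | not insufficient (max 17) |
| 5, 14, 17 | normal (17 ≥ 16) | insufficient (min 5) | insufficient (max 14) |

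The values are invented to show the logic. Each reading conflicts with 6.3.4 in at least one row. The opposite conflict is also possible in principle. On the charitable reading, a subject with C30 at or above 16 and C60 below 16 needs no further follow-up under 6.3.4.1 but must be followed to recovery under 6.3.4.

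**3. Leaving the pathway on the literal reading.** A subject must have C0 ≥ 16 and C30 ≥ 16. Entry is at 5 or less, so C0 must reach at least 16/5 = 3.2 times the entry threshold. If C0 is still 5 or less, the rule is met for certain.

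**4. How often C0 is below 16.** The documents do not say. As an illustration, assume that C0 at the test is lognormal with median m and coefficient of variation CV:

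P(C0 < 16) = Φ( ln(16/m) / σ ), with σ = √ln(1 + CV²).

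Worked case, m = 10 and CV = 100%: σ = √ln 2 = 0.833, ln 1.6 = 0.470, ratio 0.564, probability 71.4%.

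| Assumed median (µg/dL) | CV 30% | CV 50% | CV 75% | CV 100% |
|---|---|---|---|---|
| 3 | 100% | 100% | 99.4% | 97.8% |
| 5 | 100% | 99.3% | 95.9% | 91.9% |
| 8 | 99.1% | 92.9% | 85.0% | 79.7% |
| 10 | 94.5% | 84.0% | 75.9% | 71.4% |

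Medians and CVs are assumptions. Since a C30 below 16 also meets the literal rule, each entry is a lower bound for the share meeting it under that assumption.

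**5. Effect on the composite endpoint.** After baseline, every subject who enters 6.3.4.1 has cortisol of 5 or less. That is the other arm of the composite, so the subject counts as an event whichever ACTH rule is used.

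**The case against.** The strongest reply is that the conflict is a local wording slip with a narrow reach. It affects only asymptomatic subjects with low cortisol. Symptomatic subjects are handled without a test result, and scheduled tests in subjects above 5 µg/dL do not enter the pathway. No count of affected subjects is available. All of this stands and limits the reach, but it does not remove the conflict.

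A reader might infer that nearly every subject sent to the test would be prescribed hydrocortisone. The documents do not support that. It needs the literal reading of *minimum* and a cortisol distribution that they do not give. Although the low value must be "confirmed by 2 blood draws", the ACTH test can follow up to a week later, and "The ACTH stimulation test may be performed at any time of the day and does not require subjects to be in fasting state". The pre-injection sample is therefore not necessarily close to the referral value. It can be the same draw at a scheduled visit, since footnote j of Table 4-1 lets the pre-ACTH level serve as the baseline cortisol.

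A reader might also infer that the safety endpoint is distorted. It is a composite that already counts these subjects, so its percentage should barely move. Nor can one say that the 30-minute sample would be missing: the kit procedure is not in the documents, and a 60-minute test does not rule out an earlier draw.

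Finally, the plan partly handles steroid use. Protocol 5.8.2 lets subjects remain after short use for specific adverse events and captures all corticosteroid use on a dedicated form. Protocol 4.2.3 requires Sponsor approval to continue after an HPA-related event. Protocol 2.5 reports the Week 12 primary result as already known, so an amendment would act only on later data. The efficacy consequence is thus possible but unquantified.

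**Conclusion.** The inconsistency is real on either reading of *minimum*. Section 6.3.4.1 uses 0 or 30 minutes, and the definition used elsewhere for eligibility and follow-up uses 60 minutes, with the same 16 µg/dL cut-off. Its weight comes from what the sentence controls: steroid prescription and referral, the end of follow-up, ACTH-specific reporting, and exposure to an otherwise prohibited drug.

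The size is bounded only conditionally. On the literal reading the rule is met by 100% of subjects whose pre-injection value is still below 16. Those subjects make up about 71% to 100% of the pathway under assumed lognormal retest medians of 3 to 10 µg/dL and CVs of 30% to 100%. On the charitable reading the pre-injection value seldom matters and only the 30- versus 60-minute conflict remains. The wording does not settle which reading was meant. No view is taken here on which clinical rule is right.

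**What to change.** Reconcile Protocol 6.3.4.1 with 6.3.4, the synopsis, Exclusion Criterion 24 and Table 4-1 footnote r, so that one stated sampling time and one cut-off govern both management and analysis. The clinical team decides which. In the same change:

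- State whether the pre-injection value enters the rule, and replace *minimum* with wording that has one meaning.
- Align the endpoint text: <16 with ≤440 nmol/L in the synopsis, ≤16 in Protocol 6.3.6, ≤16 in SAP 17.6. Add the missing sampling time to SAP 17.6.
- State how hydrocortisone prescribed under 6.3.4.1 is treated under Protocol 5.8.2 and in the per-protocol rules of SAP 5.4.
- For subjects already handled under 6.3.4.1, list the available ACTH values by sampling time, so that any who are classified differently by the two rules can be identified.

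The cost is a protocol wording amendment with a letter to sites, a short SAP revision and one listing. The sample size and the primary analysis do not change.
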